	Stool sample (optional)							
8.9	RBR sample (saliva DNA)							

Table 1 Schedule of Activities (cont.)

Abbreviations: ADA = Anti-drug antibody; AE = Adverse event; C = Cycle; D = Day; ECOG = Eastern Cooperative Oncology Group; imAE = Immune-mediated adverse event; IMP = Investigational medicinal product; IRR = Infusion-related reaction; MUGA = Multiple-Gated Acquisition Scans; PD = Pharmacodynamic; PK = Pharmacokinetic; PRO = Patient-reported outcome; RBR = Research biosample repository; TTE = Transthoracic echocardiogram; WGS = Whole genome sequencing.

- a) During the study treatment period, assessments scheduled on the days of study treatment infusions should be performed before the start of infusion unless otherwise noted. Laboratory results have to be available prior the initiation of treatment.
- b) Vital signs include pulse rate, respiratory rate, blood pressure, and temperature at every assessment and blood oxygen saturation pre-dose at visits where tumor assessments are performed. For the first infusion, vital signs should be determined within 60 minutes before and 30 (\pm 10) minutes after the end of infusion. Vital signs will also be collected during the first infusion (every 15 [\pm 5] minutes). During subsequent infusions, vital signs should be determined within 60 minutes before the infusion, during each infusion only as clinically indicated and within 15 (\pm 10) minutes after the end of each infusion. Additional vital signs should be collected during the infusion, if clinically indicated, or if symptoms occurred with the prior infusion. Blood oxygen saturation by pulse oximetry at baseline screening and pre-dose at every visit where tumor assessments are performed.
- c) Participants who discontinue treatment for reasons other than radiographic disease progression per RECIST v1.1 (e.g., toxicity, symptomatic deterioration) will continue scheduled tumor assessments at the frequency described above until radiographic disease progression per RECIST v1.1, initiation of a new anti-cancer therapy, withdrawal of consent, death, or study termination by Sponsor, whichever occurs first. Thus, tumor assessments are to continue according to the schedule in participants who discontinue treatment for reasons other than disease progression or loss of clinical benefit.

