7.1 DISCONTINUATION OF STUDY TREATMENT

For data to be collected at the time of treatment discontinuation and follow-up and for any further evaluations that need to be completed see the SoAs in Section [1.3](#). Participants have the right to voluntarily withdraw from the study treatment at any time for any reason.

In addition, the Investigator has the right to discontinue a participant from study treatment for medical conditions that the Investigator or Sponsor determines, may jeopardize the participant's safety if he/she continues with the study treatment.

Participants must permanently discontinue study treatment if they experience any of the following:

- Intolerable toxicity related to study treatment, including development of an immune-mediated AE (imAE) determined by the Investigator to be unacceptable given the individual participant's potential response to therapy and severity of the event.
- Any medical condition that may jeopardize the participant's safety if he or she continues study treatment.
- Investigator or Sponsor determination that treatment discontinuation is in the best interest of the participant.
- Use of another non-protocol anti-cancer therapy.
- Pregnancy.
- Loss of clinical benefit as determined by the Investigator after an integrated assessment of radiographic and biochemical data, local biopsy results (if available), and clinical status (e.g., symptomatic deterioration such as pain secondary to disease).

The primary reason for study treatment discontinuation should be documented on the appropriate eCRF. Participants who discontinue study treatment prematurely will not be replaced.

Participants who discontinue study treatment will be asked to return to the clinic for treatment discontinuation visit (Section 8.11.3) ≤ 30 days after the final dose of study treatment and will undergo follow-up assessments (Section 8.11.4). The visit at which response assessment shows progressive disease may be used as the treatment discontinuation visit. Participants who discontinue study treatment for any reason other than progressive disease or loss of clinical benefit will continue to undergo tumor response assessments as outlined in the SoAs (Section 1.3) until they start a new anti-cancer therapy.

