8.1 EFFICACY ASSESSMENTS

8.1.1 Tumor and Response Evaluations

[REDACTED] Tumor assessments should be performed at the described interval regardless of treatment delays until radiographic disease progression per RECIST v1.1 ([Appendix 6](#)), initiation of a new anti-cancer therapy, withdrawal of consent, death, or study termination by the Sponsor, whichever occurs first. Thus, tumor assessments are to continue according to schedule in participants who discontinue treatment for reasons other than disease progression or loss of clinical benefit. For participants who continue treatment after progressive disease, tumor assessments are to continue according to schedule until study treatment is discontinued.

At the Investigator's discretion, tumor assessments may be repeated at any time if progressive disease is suspected. [REDACTED]

[REDACTED] Exceptions may apply at the discretion of the Investigator (e.g., in case of suspected rapid tumor growth).

Participants who are treated beyond disease progression per RECIST v1.1 will undergo tumor assessments at the frequency described above until study treatment is discontinued.

Screening assessments must include CT scans (with oral or IV contrast) or MRI scans of the chest, abdomen, pelvis, and head. A spiral CT scan of the chest may be obtained but is not a requirement. If a CT scan with contrast is contraindicated (e.g., in patients with impaired renal clearance), a non-contrast CT scan of the chest may be performed and MRI scans of the abdomen, pelvis, and head should be performed. A CT scan with contrast or MRI scan of the head must be done at screening to evaluate CNS metastasis in all patients (MRI scan must be performed if CT scan is contraindicated). An MRI scan of the head is required to confirm or refute the diagnosis of CNS metastases at baseline in the event of an equivocal CT scan. Bone scans and CT scans of the neck should also be performed if clinically indicated. If a CT scan for tumor assessment is performed in a positron emission tomography-CT scanner, the CT acquisition must be of full diagnostic quality and include CT contrast. Ultrasound and x-rays are not acceptable for monitoring target lesions. At the Investigator's discretion, other methods of assessment of measurable disease as per RECIST v1.1 may be used.

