Secondary	
ORR and DCR based on RECIST
 
ORR is defined as the proportion of participants who have achieved an objective response, characterized by a CR or PR according to RECIST v1.1. Objective response will be evaluated by treatment arm, and participants without post-baseline overall response assessments will be counted as non-responders. DCR is defined as ORR + stable disease rate (SDR).
 
An estimate of ORR for each treatment group as well as of the difference between the ORR of each experimental arm compared with the active comparator will be computed along with its 95% CI. The Mantel-Haenszel test will be used to compare the ORR of RO7247669 and the active comparator at the two-sided significance level of 20%, stratified by the protocol-defined stratification factors.
 
PFS based on RECIST
 
PFS defined as the time from randomization to the first occurrence of progression as determined by the Investigator according to RECIST v1.1 or death during the treatment period or within on study (i.e., within 60 days of the last study treatment tumor assessment) after treatment discontinuation, whichever occurs first. Participants who have not experienced disease progression at the time of analysis and who have not died during the treatment period or within 60 days of the last tumor assessment after treatment discontinuation will be censored at the time of the last tumor assessment. Participants with no post-baseline tumor assessment will be censored at the date of randomization.
 
The requirement that participants without a radiographic disease progression per RECIST v1.1 are still followed for the tumor assessments until progression or when the participant starts a new anti-cancer therapy (whatever occurs first), means that:

Endpoint	Statistical Analysis Methods

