	
- intercurrent events of treatment discontinuations in absence of disease progression per RECIST 1.1 do not per se censor the PFS observation, since the participant will still undergo tumor assessments (treatment policy strategy)
 
- intercurrent events of new anticancer therapy imply instead that the PFS observation is censored at the last available tumor assessment before the new anticancer treatment starts, therefore assuming that participants who experience this intercurrent event have the same risk as those who did not (hypothetical strategy).
 
PFS will be compared between treatment arms with use of the stratified log-rank test.
 
The HR and its 95% CI for PFS will be estimated using a stratified Cox proportional-hazards model. Kaplan-Meier methodology will be used to estimate the median PFS for each treatment arm, and Kaplan-Meier curve will be constructed to provide a visual description of the difference between treatment arms.
 
DoR based on RECIST
 
DoR is defined as the time from the first occurrence of a documented objective response to disease progression according to RECIST v1.1 or death from any cause, whichever occurs first.
 
The analysis of DoR will include only participants who achieved an objective response to study treatment. DoR will be estimated using the Kaplan-Meier methodology. As the determination of DoR is based on a non-randomized subset of participants, no formal hypothesis testing will be performed.
 
Proportion of participants reporting clinically meaningful improvements in PRO measures
 
The proportion of participants in each treatment group reporting clinically meaningful improvement (defined as ≥ 10 points) in global health status/quality of life, emotional functioning, social functioning and dysphagia as measured by the EORTC QLQ-C30, IL-97, and OES-18 will be computed.
 
An estimate of this proportion for each treatment group as well as of the difference between proportions of each experimental arm compared to the active comparator will be computed along with its 95% CI.

CI = Confidence interval; CR = Complete response; DCR = Disease control rate; DoR = Duration of response; EORTC = European Organisation for Research and Treatment of Cancer; HR = Hazard ratio; IL97 = Item Library 97; OS = Overall survival; PFS = Progression-free survival; PR = Partial response; PRO = Patient-reported outcomes; RECIST = Response evaluation criteria in solid tumors.

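### Table 9 calls PFS handling of treatment discontinuation treatment policy because scans continue, but the scan rules conflict on participants who stop for loss of clinical benefit

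*Combined protocol and SAP*

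**What the plan says.** **Table 9 (Section 9.3.2).** For PFS, "intercurrent events of treatment discontinuations in absence of disease progression per RECIST 1.1 do not per se censor the PFS observation". The ground given is that "participants without a radiographic disease progression per RECIST v1.1 are still followed for the tumor assessments until progression", or until a new anti-cancer therapy starts. The handling is labelled treatment policy, with no exception for loss of clinical benefit. A participant without documented progression is censored at the last tumor assessment, unless death occurs in the treatment period or within 60 days of the last assessment after discontinuation.

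**Sentences that make an exception.** Section 7.1: "Participants who discontinue study treatment for any reason other than progressive disease or loss of clinical benefit will continue to undergo tumor response assessments". Section 8.1.1: "tumor assessments are to continue according to schedule in participants who discontinue treatment for reasons other than disease progression or loss of clinical benefit". Sections 1.1, 4.1 and 8.11.4 and the second sentence of Table 1 footnote c say the same. Section 7.1 makes loss of clinical benefit a mandatory reason to stop treatment. It is judged by the investigator from imaging, biochemistry, biopsy and clinical status, does not require RECIST progression, and has symptomatic deterioration as its example.

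**Sentences that point to continued scanning.** The first sentence of Table 1 footnote c: "Participants who discontinue treatment for reasons other than radiographic disease progression per RECIST v1.1 (e.g., toxicity, symptomatic deterioration) will continue scheduled tumor assessments". In Sections 1.1, 4.1 and 8.1.1, the list of events that end tumor assessments is RECIST progression, new anti-cancer therapy, consent withdrawal, death or study termination; loss of clinical benefit is not on it. Appendix 6 (Special Notes on Response Assessment) asks sites to try to document objective progression after treatment has stopped for symptomatic deterioration.

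**The concern.** The treatment-policy label rests entirely on continued scanning. If a site reads the exception literally, a participant who stops for loss of clinical benefit without RECIST progression has no further scheduled scans. Progression can then no longer be detected. The 60-day death window, which runs from the last scan, is also fixed at that point.

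The participant is then censored at a scan that showed no progression, at a time when the investigator has judged that the disease is no longer controlled. Kaplan-Meier and Cox methods treat that participant as having the same future risk as those still followed, which is doubtful here. Table 9 states this equal-risk assumption openly for censoring at new anti-cancer therapy and calls it a hypothetical strategy. For loss of clinical benefit the same mechanism can operate with no stated assumption, under a different label.

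What is at stake is the interpretation of PFS, a secondary endpoint. Because the conflict concerns data collection, a later analysis plan can relabel the estimand but cannot recover scans that were never taken.

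**Working it through.** **1. Text comparison.** Take a participant who stops for symptomatic deterioration without RECIST progression.

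- Table 9: scanned until progression or new therapy.
- Footnote c, first sentence: scanned.
- Stopping lists in Sections 1.1, 4.1 and 8.1.1: scanned.
- Exception sentences in Sections 1.1, 4.1, 7.1, 8.1.1 and 8.11.4, and footnote c, second sentence: not required, if the stop is recorded as loss of clinical benefit.

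Two sites can both follow the protocol and treat the same participant differently. This step needs no assumption.

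**2. How often censoring would follow.** The plan gives no figure to reproduce: the readable text has no PFS event count, power or alpha, and the scan interval is redacted. As an illustration, assume exponential survival after loss of clinical benefit with median m months, and a last scan lag days before the stop. The share not dying within the 60-day window, and so censored, is

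2^(−(60 − lag) / (30.4375 × m))

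- m = 1, lag = 0: 2^(−60/30.4375) = 0.26
- m = 2, lag = 0: 2^(−60/60.875) = 0.51
- m = 2, lag = 21: 2^(−39/60.875) = 0.64
- m = 4, lag = 0: 2^(−60/121.75) = 0.71
- m = 6, lag = 42: 2^(−18/182.625) = 0.93

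The range over m from 1 to 6 months and lag from 0 to 42 days is 26% to 93%. The share of an arm that stops for loss of clinical benefit without RECIST progression is not in the documents. At an assumed 10% to 20%:

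- low: 0.10 × 0.26 = 0.026, about 3% of an arm
- high: 0.20 × 0.93 = 0.186, about 19% of an arm

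**3. What it could do to the hazard ratio.** The simulation used 4,000 participants per arm. Assumed inputs: median time to true progression 2 months in control, median survival after progression 4 months, scans every 6 or 8 weeks, and 15% or 30% stopping for loss of clinical benefit at the moment of true progression. There was no other censoring. Each line compares continued with stopped scanning on the same simulated participants; the ranges cover both scan intervals.

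- Equal shares: HR changed by at most 0.02 (for example 0.75 to 0.73), although 12% to 25% of all participants were censored.
- 30% control, 15% experimental: for true HR 1.0, 0.99 to 1.11 and 1.01 to 1.12; for true HR 0.75, 0.75 to 0.83 and 0.73 to 0.82.
- 15% control, 30% experimental: for true HR 1.0, 1.00 to 0.88 and 1.01 to 0.90; for true HR 0.75, 0.79 to 0.69 and 0.77 to 0.68.

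With unequal shares the shift is 0.08 to 0.12, towards the arm with more such stops. The simulated shares are larger than those in step 2, and every such stop coincides with true progression, so this is a demanding case.

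**The case against.** The strongest reply is that no sentence orders scans to stop at loss of clinical benefit. The stopping lists omit it, the exception in Sections 1.1, 4.1 and 8.1.1 reads as a gloss on those lists, and footnote c and Appendix 6 favour scanning. That stands against any claim that the protocol uniformly ends scans. It does not remove the conflict, because Sections 7.1 and 8.11.4 state the exception on its own.

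A reader might infer that the sickest participants are the ones censored. The documents do not support this: death on treatment or within 60 days of the last scan is a PFS event, so those who die soonest are the most likely to count. Those at risk of censoring outlive the window without documented progression.

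A reader might also infer that toxicity in an arm drives the censoring. Footnote c names toxicity as a reason for which scans continue, and investigators and participants are blinded. No mechanism for a difference between arms is shown.

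The affected group may be small. Treatment may continue beyond RECIST progression (Section 7.1.1), so many stops for loss of benefit will follow a progression already counted. Appendix 3, Section 9, describes progression determined from symptoms as rare. This stands, and is why the 10% to 20% is only an assumption.

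Finally, Section 9.3 leaves further detail to a separate technical document, so it cannot be said that no sensitivity analysis is planned.

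**Conclusion.** The inconsistency is real and can be verified from the text alone. Table 9 justifies a treatment-policy strategy by scans that other sections do not consistently require after loss of clinical benefit. Participants who stop for that reason without RECIST progression can be censored at the last scan, and that censoring is potentially informative.

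The size is uncertain. The estimate of about 3% to 19% of an arm rests on an assumed share of stops, assumed survival after stopping and an assumed interval since the last scan. The effect on the hazard ratio is negligible in the simulation if the arms are alike, and about 0.08 to 0.12 if they differ as assumed; the direction cannot be predicted from the documents.

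It is tempting to say that duration of response has the same gap. It does not: death from any cause counts there with no 60-day window, so the effect is limited to progression that is missed or recorded late. OS is unaffected, PFS is secondary, and the estimand in Table 4 covers only OS. The point is worth correcting, but it does not threaten the primary analysis.

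**What to change.** Reconcile Sections 1.1, 4.1, 7.1, 8.1.1 and 8.11.4 and both sentences of Table 1 footnote c with each other and with Table 9. Either of two routes would do:

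- state a single tumor-assessment rule, in the same words throughout, that matches Table 9's premise; or
- keep an exception, name discontinuation for loss of clinical benefit without RECIST progression as a separate PFS intercurrent event with its own stated strategy, and limit the treatment-policy label to the other discontinuations.

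Under either route, specify a PFS sensitivity analysis that counts discontinuation for loss of clinical benefit without RECIST progression, and later deaths, as events. Section 7.1 already has the primary reason for discontinuation recorded on the eCRF, so no new data item is needed. Reporting the number of such stops by arm would show whether the shares differ.

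The cost is protocol wording, one extra analysis and, under the first route, possibly some follow-up scans that the first sentence of footnote c already calls for.

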9.3.3 Safety Analyses

All safety analyses will be based on the safety analysis population grouped according to the treatment assigned at randomization ([Table 10](#)).

Safety analyses will include all participants randomized to study treatment and who received any amount of the study treatment, whether prematurely withdrawn from the study or not. Safety analyses will be performed by treatment arm and will be based on actual treatment received. Drug exposure will be summarized, including duration.

Verbatim description of AEs will be mapped to the MedDRA terms. Severity for all AEs will be graded by the Investigator according to the NCI CTCAE v5.0. All AEs will be

summarized by treatment arm and NCI CTCAE grade. In addition, SAEs and AEs leading to study treatment discontinuation or interruption will be summarized accordingly. Multiple occurrences of the same event will be counted once at the maximum severity. Laboratory data with values outside of the normal ranges will be identified. In addition, selected laboratory data, including ADA results, will be summarized by treatment arm. Deaths and causes of deaths will be summarized.

Table 10 Safety Statistical Analysis Methods

Endpoint	Statistical Analysis Methods
Adverse events	The original terms recorded on the eCRF by the Investigator for AEs will be coded by the Sponsor. Adverse events will be summarized by mapped term and appropriate thesaurus level.
Clinical laboratory tests	All clinical laboratory data will be stored on the database in the units in which they were reported. Laboratory test values will be presented in International System of Units (SI units; Système International d'Unités) by individual listings with flagging of abnormal results. Shifts in NCI CTCAE v5.0 grades from baseline to the worst grade observed during treatment and summary tables of change from baseline over time based on SI units will be presented for selected laboratory parameters. Individual participant listings (abnormal values or out of range) will be produced. For details on standard reference ranges and data transformation and the definition of laboratory abnormalities, see Appendix 4 . Additional figures/tables/listings will be produced as deemed appropriate.
Vital signs	Vital signs data will be presented by individual listings with flagging of values outside the normal ranges and flagging of abnormalities. In addition, tabular summaries will be used, as appropriate.
ECG data analysis	ECG data will be presented by individual listings. In addition, tabular summaries will be used, as appropriate.
Concomitant medications	The original terms recorded on the participants' eCRF by the Investigator for concomitant medications will be standardized by the Sponsor by utilizing a mapped term and appropriate drug dictionary level. Concomitant medications will be presented in summary tables and listings.

AE = Adverse event; ECG = Electrocardiogram; eCRF = Electronic case report form;
NCI CTCAE = National Cancer Institute Common Terminology Criteria for Adverse Events;
SI units = *Système International d'Unités*.

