3. OBJECTIVES AND ENDPOINTS

The primary objective is expressed in the estimand framework through the 5 attributes as described in [Table 4](#).

Table 4 Estimands

Attribute	Study Definitions
Population	Patients with unresectable advanced or recurrent ESCC who are refractory or intolerant to one prior line of chemotherapy
Primary endpoint (variable)	Overall survival
Treatments	
 Experimental: 2100 mg Q2W RO7121661 Experimental: 2100 mg Q2W RO7247669 Active comparator: 240 mg Q2W nivolumab
Intercurrent events and their handling	New anti-cancer therapy and treatment discontinuation, handled via treatment policy (intercurrent event is ignored)
Summary measure	Hazard ratios

The objectives and corresponding endpoints are provided in [Table 5](#).

Table 5 Objectives and Endpoints

Objectives	Endpoints
Primary	
To evaluate the efficacy of RO7247669 compared with nivolumab.	
 OS, defined as the time from randomization to death from any cause
Secondary	
To evaluate the safety and tolerability of RO7121661 and RO7247669 compared with nivolumab.	
 Nature, frequency, and severity of adverse events (AEs) graded according to the National Cancer Institute (NCI) Common Terminology Criteria for Adverse Events (CTCAE) v5.0
To evaluate the efficacy of RO7247669 compared with nivolumab.	
 Objective response rate (ORR), defined as the proportion of participants with an objective response (i.e., complete response [CR] or partial response [PR]), according to RECIST v1.1 Disease control rate (DCR), defined as ORR + stable disease rate (SDR) Duration of response (DoR) for participants with ORR, defined as the time from the first occurrence of a documented objective response to disease progression according to RECIST v1.1 or death from any cause, whichever occurs first Progression-free survival (PFS) defined as the time from randomization to the first occurrence of progression as determined by the Investigator according to RECIST v1.1 or death during the treatment period or within 60 days of the last tumor assessment after treatment discontinuation from any cause, whichever occurs first Proportion of participants reporting clinically meaningful improvement in global health status/quality of life, emotional functioning, social functioning and dysphagia

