8.3 ADVERSE EVENTS AND SERIOUS ADVERSE EVENTS

The definitions of an AE or SAE can be found in [Appendix 2](#). The NSAESI and disease-related events and/or disease-related outcomes not qualifying as AEs or SAEs are discussed in Section [8.3.6](#) and Section [8.3.7](#).

The Investigator and any qualified designees are responsible for ensuring that all AEs (including assessment of seriousness, severity and causality; see [Appendix 2](#)) are

recorded on the Adverse Event eCRF and reported to the Sponsor in accordance with instructions provided in this section and in [Appendix 2](#).

Procedures used for recording AEs are provided in [Appendix 3](#):

8.3.1 Time Period and Frequency for Collecting Adverse Event and Serious Adverse Event Information

The method of recording, evaluating, and assessing causality of AEs and SAEs and the procedures for completing and transmitting SAE reports are provided in [Appendix 2](#).

Investigators will seek information on AEs at each participant's contact. All AEs, whether reported by the participant or noted by study personnel, will be recorded in the participant's medical record and on the Adverse Event eCRF as follows:

After informed consent has been obtained **but prior to initiation of study treatment**, only SAEs caused by a protocol-mandated intervention should be reported (e.g., SAEs related to invasive procedures such as biopsies). Any other AE should not be reported.

After initiation of study treatment, all AEs, regardless of relationship to study treatment, will be reported until 30 days after the final dose of study treatment or until initiation of new systemic anti-cancer therapy, whichever occurs first. SAEs will continue to be reported until 90 days after the final dose of study treatment or until initiation of new systemic anti-cancer therapy, whichever occurs first. In addition, AEs of special interest will continue to be reported until 90 days after the final dose of study treatment, regardless of initiation of new systemic anti-cancer therapy.

Post-study AEs and SAEs: The Investigator is not required to actively monitor participants for AEs after the end of the AE reporting period.

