9.3.8.1 Exploratory Analyses of PRO-CTCAE

PRO-CTCAE analyses will be primarily descriptive, with a focus on characterizing the pattern of symptomatic treatment toxicities over the course of the study. Results from these exploratory analyses will be presented separately from the other safety analyses. PRO-CTCAE data will be analyzed at the item level in line with current NCI recommendations for data handling ([Basch et al. 2014](#)).

PRO-CTCAE data will be summarized over time. The proportion of missing data at each assessment time-point will also be summarized to facilitate interpretation of data.

The number and percentage of participants reporting each symptom and the change from baseline by category (frequency of occurrence, severity, interference) will be summarized at each assessment time-point by treatment arm. For items that are rated on a 5-point Likert scale, the maximum post-baseline score and change from baseline will be summarized by treatment arm.

Graphical representation of PRO-CTCAE data over time will also be provided.

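### Worst-ever AE counts and maximum PRO-CTCAE scores depend on time on treatment; add fixed-time cumulative incidence so that unequal durations cannot be read as unequal toxicity

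*Combined protocol and SAP*

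**What the plan says.** Safety is a comparative secondary objective in Table 5: "To evaluate the safety and tolerability of RO7121661 and RO7247669 compared with nivolumab". Its endpoint is "Nature, frequency, and severity of adverse events (AEs) graded according to the National Cancer Institute (NCI) Common Terminology Criteria for Adverse Events (CTCAE) v5.0", with no time or exposure denominator.

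Section 9.3.3 has AEs "summarized by treatment arm and NCI CTCAE grade", under the counting rule "Multiple occurrences of the same event will be counted once at the maximum severity". Drug exposure, including its duration, is described separately. Laboratory tables follow the same worst-ever logic: "Shifts in NCI CTCAE v5.0 grades from baseline to the worst grade observed during treatment".

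Under Section 8.3.1, AEs "will be reported until 30 days after the final dose of study treatment or until initiation of new systemic anti-cancer therapy, whichever occurs first". SAEs run to 90 days after the last dose or to new systemic therapy. AEs of special interest run to 90 days regardless of new therapy. Every window is therefore anchored to the last dose. Sections 4.1 and 4.1.1 allow treatment to continue while there is clinical benefit, for at most 24 months.

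For PRO-CTCAE items on the five-point scale, Section 9.3.8.1 states that "the maximum post-baseline score and change from baseline will be summarized by treatment arm". It also plans summaries at each time-point, graphs over time and the proportion of missing data. Table 3 schedules a form on Day 1 of every cycle, on Day 8 of Cycles 1 to 5, at discontinuation and at the first follow-up only.

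**The concern.** A proportion with at least one event, or a maximum over repeated forms, rises with the length of observation. Here that length is partly an outcome of treatment: Section 4.1.4 sets out the hypothesis that RO7247669 prolongs survival relative to nivolumab, and a more effective drug may well be given for longer. A difference between arms in the planned tables could then mix toxicity with duration, and nothing in Section 9.3.3 separates the two. Tabulating exposure warns the reader but does not allow a crude percentage to be converted into a risk over a common period. At stake is the reading of tolerability against an active comparator.

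**Working it through.** The plan gives no figure to reproduce, so the check asks what the stated summaries would show if the two arms were equally toxic.

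**Inputs.** From the documents: the 30-day AE window, the 24-month cap and the Table 3 schedule. Assumed: exponential treatment time with medians of 3 versus 4.5 months (also 3 versus 6), hazards of 0.05 to 0.30 first events per month, and no link between treatment time and AE risk.

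**1. Persistent hazard.** Let μ = ln 2 / median, let λ be the AE hazard, and let f = 30/30.4 = 0.987 months. The crude proportion with an event is

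P = 1 − e^(−λf) × [ μ/(μ+λ) × (1 − e^(−24(μ+λ))) + e^(−24(μ+λ)) ].

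At λ = 0.10, e^(−λf) = 0.906.
- Median 3 months: μ = 0.231, the bracket is 0.698, and P = 1 − 0.906 × 0.698 = 36.8%.
- Median 4.5 months: μ = 0.154, the bracket is 0.607, and P = 1 − 0.906 × 0.607 = 45.0%.

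| λ per month | 3 months | 4.5 months | Ratio |
|---|---|---|---|
| 0.05 | 21.7% | 28.0% | 1.29 |
| 0.10 | 36.8% | 45.0% | 1.22 |
| 0.20 | 56.0% | 64.3% | 1.15 |
| 0.30 | 67.6% | 74.8% | 1.11 |

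At 3 versus 6 months the ratios run from 1.52 down to 1.17.

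**2. Early hazard only.** With λ = 0.10 for the first 2 months and zero afterwards, crude incidence is 17.2% versus 17.5% at 3 versus 4.5 months, a gap of 0.3 points.

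**3. Exposure-adjusted rate** (first events divided by person-time to first event or end of window). With the persistent hazard it returns 0.100 per month in both arms. With the early hazard, mean person-time is 4.51 versus 6.15 months. The rates are 0.172/4.51 = 0.0381 and 0.175/6.15 = 0.0285, a ratio of 0.75. At 3 versus 6 months the ratio is 0.61. The longer-treated arm now looks safer with no true difference.

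**4. Cumulative incidence at 3 months**, censoring at the end of the reporting window. The target is 1 − e^(−0.3) = 25.9% with the persistent hazard and 1 − e^(−0.2) = 18.1% with the early hazard. Simulation gives 25.9% and 18.1% in both arms. This is the only one of the three summaries that is right under both hazard shapes.

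**5. PRO-CTCAE.** After c cycles the number of post-baseline forms is min(c,5) + (c − 1) + 2: that is 5, 9 and 19 forms after 2, 4 and 13 cycles. The assumed score is a latent normal with mean 0.6, between-participant SD 0.8 and within-participant SD 0.4 to 0.6, rounded to 0–4, with no true change and all forms completed. At arm medians of 3 versus 4.5 months:
- maximum score ≥3: 6.8% versus 7.5% (SD 0.4) and 14.8% versus 16.7% (SD 0.6);
- maximum above the single baseline form: 52.1% versus 55.4% and 66.5% versus 69.9%.

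A second score model (category shares 60/25/10/4/1%, within-person correlation 0.8, 0.5 and 0.3) gives 16.1 versus 17.5%, 27.1 versus 30.5% and 34.6 versus 39.4% for maximum ≥3. The direction is the same, with gaps of 1.4 to 4.8 points.

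**The case against.** Several points on the other side stand.

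- The distortion needs both unequal durations and a hazard that persists. The documents establish neither, and Section 8.3.7.1 describes infusion reactions as mainly a first-infusion problem. A reader might infer that the longer-treated arm will look more toxic whatever the event; step 2 shows that this does not follow.
- Events during longer treatment are real. Crude incidence over the regimen as given is a legitimate description, and Section 9.3.3 plans no formal safety test. The risk is misreading, not an inflated error rate.
- A reader might infer that excess toxicity in an arm stopped early would go unseen. Section 9.3.3 separately summarises SAEs, AEs leading to discontinuation or interruption, deaths and exposure, so that is too strong.
- A reader might take 9 versus 19 forms as the contrast between arms. Those counts describe individuals after 4 and 13 cycles; at arm level the effect is what step 5 shows. PRO-CTCAE is also exploratory in Table 5 and already shown by time-point.
- Section 9.3 defers detail to a separate technical document that is not among those reviewed. A time-adjusted analysis may exist there; what can be said is that Sections 9.3.3 and 9.3.8.1 name none.

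None of this corrects the crude AE proportions or the maximum-score table when durations do differ.

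**Conclusion.** The point holds in a conditional form. As written, the AE and maximum PRO-CTCAE summaries cannot separate toxicity from time under observation. With a persistent hazard of 0.05 to 0.30 per month and medians of 3 versus 4.5 months, equal toxicity produces crude ratios of 1.11 to 1.29. With events confined to the first 2 months the difference is under 1 point. For PRO-CTCAE the artefact is about 1 to 2 points for a maximum ≥3 (up to about 5 under the second score model) and 3 to 4 points for scores above baseline. The worst-grade laboratory shifts depend on duration in the same way, but their size was not calculated.

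All magnitudes rest on assumed durations, hazards and score distributions. The documents do not support the stronger conclusion that the planned tables will misstate the comparison, nor that exposure-adjusted rates should replace the crude percentages: step 3 shows that such rates can mislead by more than the problem they are meant to solve. This is an inexpensive improvement to a descriptive comparison, not a defect in the primary analysis.

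**What to change.** **Section 9.3.3.** Keep the crude tables. For RO7247669 versus nivolumab, add cumulative incidence of first AE, first Grade ≥3 AE and first SAE at fixed times, for example 3 and 6 months. Censor at the end of each participant's reporting window for that event type (30 or 90 days after last dose, or new systemic therapy where it applies) and treat death as a competing event. Show exposure-adjusted rates, if at all, only as a supplement, with a note that they assume a roughly constant hazard.

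**Section 9.3.8.1.** Beside the planned maximum, add the maximum over a common early window, Cycle 1 Day 8 to Cycle 5 Day 8, with the number of forms contributing in each arm. This reduces the imbalance but does not remove it for participants who stop before Cycle 5, so the form counts matter.

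**Cost.** SAP wording and a few extra tables from dates and forms already collected, best settled before unblinding. Late events remain described only by the crude and by-visit summaries. The cumulative incidence also assumes that stopping treatment is unrelated to later AE risk, which should be stated with the tables. If the technical document already contains such an analysis, a cross-reference in Section 9.3.3 is enough for the AE part.
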